5.3 Lifestyle Considerations

Participants must adhere to protocol-prescribed procedures to avoid pregnancy. This includes monthly pregnancy tests after start of treatment and reliable use of acceptable effective contraceptive methods.

Excessive tobacco uses and smoking has been restricted based on the Investigator's discretion. Abuse of alcohol is prohibited. Alcohol intake should be limited to 2 to 3 units per day, not to exceed 14 units per week. Active use of illicit drugs is prohibited.

Note: CCI

CCI

Refer to [Table 2](#) for a list of

prohibited medications.

Participants must refrain from consumption of grapefruit, grapefruit juice, Seville oranges, Seville orange marmalade, and Seville orange juice or other products containing grapefruit or Seville oranges from 14 days prior to the first dose of study treatment and for the duration of the study treatment (ie, final dose).

5.4 Screen Failures

Screen failures are defined as participants who consent to participate in the clinical study but are not subsequently allocated to treatment in the study CCI. A minimal set of screen failure information is required to ensure transparent reporting of screen failure participants to meet the Consolidated Standards of Reporting Trials publishing requirements and to respond to queries from regulatory authorities. Minimal information includes demographic data, reason for screen failure, and any AEs or SAEs meeting reporting requirements as outlined in the data entry guidelines.

Individuals who do not meet the criteria for participation in this study (screen failure) may not be rescreened except for; participants with diagnosis and treatment of chlamydia, gonorrhea, or trichomonas, if not at risk for reinfection; simple ovarian cyst adequately treated among other. Please refer to [Section 5.2](#) for complete details. Participants may be rescreened on a case-by-case basis after discussion and approval by the Medical Monitor.

Rescreened participants retain the same participant number ([Appendix 2](#)). If the rescreening is outside the 42-day window since V1, all screening assessments must be repeated.

6.0 STUDY TREATMENT AND CONCOMITANT THERAPY

Study treatment is defined as any investigational intervention(s), marketed product(s), Placebo, or medical device(s) intended to be administered to a study participant according to the study protocol.

6.1 Study Treatments Administered

Details of the treatments administered in this study (OG-6219 and Placebo to match OG-6219) are presented in [Table 3](#).

Table 3 Study Treatment Administered

Study Treatment Label	OG-6219 CCI or Placebo	
Study Treatment Name	OG-6219	Placebo to match OG-6219
Type	Investigational	Placebo
Dose Formulation	White to off-white to light brown tablet, with or without mottling	White to off-white to light brown tablet, with or without mottling
Unit Dose Strength(s)	CCI	Not Applicable
Dosage	BID, arm dependent	Not Applicable
Route of Administration	Oral	Oral
Fill Counts	Bottle A: CCI Bottle B:	Bottle A: CCI Bottle B:
Dosing Instructions	Bottle A: CCI BID as directed. Bottle B: BID as directed.	Bottle A: CCI BID as directed. Bottle B: BID as directed.
Use	Experimental	Placebo
Sourcing	Provided centrally by the Sponsor	Provided centrally by the Sponsor
Packaging and Labeling	Study treatment will be provided in bottles containing CCI labeled as “OG-6219 CCI or Placebo” to maintain the blind. The bottles will also be labeled as required per country requirements. Provided centrally by the Sponsor	Placebo will be provided in bottles containing either CCI labeled as “OG-6219 CCI or Placebo” to maintain the blind. The bottles will also be labeled as required per country requirements. Provided centrally by the Sponsor
Storage	CCI	

Abbreviations: BID=twice a day; V=visit.

Table 4 Treatment Arms

Treatment Arm Type	Placebo	OG-6219 CCI BID (Experimental)	OG-6219 CCI BID (Experimental)	OG-6219 CCI BID (Experimental)
Arm Treatment Description	Participants will receive OG-6219 CCI BID. Refer to Table 5 for dosing details.	Participants will receive OG-6219 CCI BID during double-blind Treatment Period. Refer to Table 5 for dosing details.	Participants will receive OG-6219 CCI BID during double-blind Treatment Period. Refer to Table 5 for dosing details.	Participants will receive OG-6219 CCI BID during double-blind Treatment Period. Refer to Table 5 for dosing details.

Abbreviations: BID=twice a day; V=visit.

Table 5 Blinded Study Treatment Overview

	Bottle A—OG-6219 CCI or Placebo		Bottle B—OG-6219 CCI or Placebo	
Treatment Arm	OG-6219 CCI Active	OG-6219 CCI Placebo	OG-6219 CCI Active	OG-6219 CCI Placebo
OG-6219 Placebo BID	CCI BID	CCI BID	CCI BID	CCI BID
OG-6219 CCI BID	CCI BID	CCI BID	CCI BID	CCI BID
OG-6219 CCI BID	CCI BID	CCI BID	CCI BID	CCI BID
OG-6219 CCI BID	CCI BID	-	CCI BID	CCI BID
OG-6219 Placebo BID	CCI BID	CCI BID	CCI BID	CCI BID

Abbreviations: BID=Twice a day.

Each participant will be dispensed 4 bottles (2 x Bottle A and 2 x Bottle B) for each treatment period to support up to CCI of dosing.

Bottle A will contain C OG-6219 CCI or Placebo tablets and Bottle B will contain C OG-6219 CCI or Placebo tablets.

Blinded doses are achieved by taking CCI from Bottle A (BID) and CCI from Bottle B (BID).

Table 6 Non-Investigational Medicinal Products / Rescue Medication

Medication Name:	Naproxen sodium
Type	Non-investigational medicinal product: Rescue medication
Dosage Formulation:	Tablet
Unit Dose Strength:	CCI
Route of Administration:	Oral
Dosing Instructions:	Take as directed.
Packaging and Labeling	Product will be provided in commercial packaging and will be labeled as required per country requirements.
Sourcing:	Provided centrally by the Sponsor. In special circumstances, may be provided locally with prior approval from the Sponsor.

6.2 Preparation, Handling, Storage, and Accountability

- The Investigator or designee must confirm appropriate temperature conditions have been maintained during transit for all study treatment received, and any discrepancies are reported and resolved before use of the study treatment.
- Only participants enrolled in the study may receive study treatment, and only authorized study site staff may supply or administer study treatment. All study treatment must be stored in a secure, environmentally controlled, and monitored (manual or automated) area in accordance with the labeled storage conditions with access limited to the Investigator and authorized study site staff.
- The Investigator, institution, or the head of the medical institution (where applicable) is responsible for study treatment accountability, reconciliation, and record maintenance (ie, receipt, reconciliation, and final disposition records).
- For reporting of potential quality-related concerns with study treatments, refer to the Pharmacy Manual. Further guidance and information for the final disposition of unused study treatment are provided in the Pharmacy Manual or other specified location.

The Investigator, a member of the study site staff, or a hospital pharmacist must maintain an adequate record of the receipt and distribution of all study treatment using the Drug Accountability Form. These forms must be available for inspection at any time.

For further details, see current OG-6219 IB.

6.3 Measures to Minimize Bias: Randomization and Blinding

Randomization will be used to avoid bias in the assignment of participants to treatment groups. Eligible participants will be randomized in a CCI ratio at Randomization Visit CCI to receive one of 3 doses of OG-6219 or matching Placebo. CCI participants will be randomized to CCI the 4 study arms.

Participants will sign a separate consent for optional intensive PK prior to randomization. The study will be stratified based on consent to intensive PK (Yes/No) in order to ensure balanced treatment assignment within the intensive PK group.

The study site will contact the Interactive Response Technology (IRT) system to obtain the study treatment. Study treatment will be dispensed at the study visits summarized in the SoA (Section 1.3). Before the study is initiated, additional IRT directions and/or log in information will be provided to each study site.

Method of blinding:

The study is blinded for assignment of OG-6219 and Placebo. Tablets of OG-6219 and Placebo will appear identical.

The IRT will be programmed with blind-breaking instructions. In case of an emergency, the Investigator has the sole responsibility for determining if unblinding of a participant's treatment assignment is warranted.

Participant safety must always be the first consideration in making such a determination. If the Investigator decides that unblinding is warranted, he/she may, at his/her discretion, contact the Sponsor/designee to discuss the situation prior to unblinding a participant's treatment assignment unless this could delay emergency treatment of the participant.

If a participant's treatment assignment is unblinded, the Sponsor must be notified within 24 hours after breaking the blind. The date and reason that the blind was broken must be recorded in the source documentation and electronic case report form (eCRF), as applicable.

During the double-blind period, the following personnel will remain blinded to the treatment assignment: participants, Investigators, other study site personnel, clinical staff, Medical Monitor, study site monitors and other Sponsor representatives involved in the clinical aspects of the study conduct.

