9.4.2 Primary Endpoint Analysis

The primary endpoint will be the mean change from BC of the average daily OPP score during TRC3. The OPP will be calculated for each cycle as the total of OPP scores reported during the cycle divided by the number of days during the cycle in which the score was reported. For participants who discontinue early, their last cycle will be associated with the cycle number at entry into the cycle. The primary analysis will be conducted using the MFAS and will use a longitudinal model. The response vector for the model will be change from BC in the average OPP during TRC1, TRC2, and TRC3. Model terms will include the respective baseline, treatment, time (ie, cycle), and treatment-time interaction, allowing for the inclusion of individual outcomes over time (cycle). An unstructured error structure will be assumed. If

nonconvergence is encountered, compound symmetry (CS) and first-order autoregressive AR(1) error structures will be considered.

Least squares mean change from baseline for each treatment group, with corresponding standard errors will be provided. Estimated treatment differences (each active treatment group versus Placebo) with corresponding 95% CI and 2-sided p-values will also be provided for each active treatment group. No missing data will be imputed for the primary analysis.

Supportive analyses will be conducted using an analysis of covariance (ANCOVA) on the change from baseline to the TRC3, with treatment as a fixed factor and baseline OPP as a covariate.

The primary longitudinal and ANCOVA models will be repeated using the PP set.

A completers analysis will be performed for those participants who completed all 3 treatment cycles. Details regarding additional sensitivity and subgroup analyses of the primary efficacy endpoint will be described in the SAP.

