## 5. COVARIATES AND SUBGROUPS

### 5.1. Planned Covariates and Factors

The statistical analyses will include treatment, time, and treatment-by-time interaction as factors (if only one timepoint is included in the analysis, treatment will be the only factor). The baseline value of the endpoint will be included as a covariate (for endpoints where a baseline value exists).

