#### 8.3.5. Analysis of Primary Efficacy Endpoint

The primary endpoint will be analysed using a longitudinal model, i.e. a Mixed Models for Repeated Measures (MMRM), fitted to data from all participants with a post-treatment OPP measurement. The response vector for the model will be the change from BC in the mean OPP during TRC1, TRC2, and TRC3. Model terms will include the baseline cycle value (mean OPP for BC), treatment, time (i.e., cycle), and treatment-by-time interaction. An unstructured error structure will be assumed. If nonconvergence under the UN assumption is encountered a compound symmetry (CS) and autoregressive AR(1) error structures will be assumed in sequence. Estimated treatment differences (each OG-6219 treatment group versus

Placebo) with corresponding 95% CI and 2-sided p-values will be derived from the model for each treatment cycle.

Analysis using MMRM method will be implemented using the SAS® procedure MIXED as follows (example code only):

```
PROC MIXED DATA = ...;  
  CLASS CYCLE TREATMENT SUBJID;  
  MODEL CHG = BASELINE TREATMENT CYCLE TREATMENT*CYCLE /  
    DDFM=KR;  
  REPEATED CYCLE / SUBJECT = SUBJID TYPE=UN;  
  LSMEANS TREATMENT*CYCLE / PDIFF CL;  
RUN;
```

where CHG = change from baseline at each treatment cycle

TREATMENT = randomized treatment group (CCI BID, CCI BID, CCI BID, and placebo)

BASELINE = baseline cycle value

CYCLE = treatment cycle

SUBJID = subject ID

In addition, the mean OPP will be summarized by cycle and treatment group using descriptive statistics of observed data and change from baseline cycle values. Mean OPP by cycle will also be presented in listings.

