### 8.3.7. Supplementary Analyses for Primary Efficacy Endpoint

Two supplementary analyses will be performed for the MFAS, both using analysis of covariance (ANCOVA) models on the change from baseline to TRC3 with treatment as a fixed factor and baseline OPP as a covariate. In the first analysis, only subjects with data from TRC3 will be included. In the second analysis, subjects without data from TRC3 will have their TRC3 value imputed using last observation carried forward (i.e. the last available of the TRC2 and TRC1 values will be used.)

Estimated treatment differences (each OG-6219 treatment group versus Placebo) with corresponding 95% CI and 2-sided p-values will be derived from the model.

Analysis using an ANCOVA model will be implemented using the SAS® procedure MIXED as follows (example code only):

```
PROC MIXED DATA = ...;  
  CLASS TREATMENT;  
  MODEL CHG = BASELINE TREATMENT;  
  LSMEANS TREATMENT / PDIFF CL;  
RUN;
```

where CHG = change from baseline to TRC3

TREATMENT = randomized treatment group (CCI BID, CCI BID, CCI BID, and placebo)

BASELINE = baseline cycle value

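### Randomisation is stratified by intensive-PK consent, but no efficacy model includes that factor; the cost is a little precision, in the conservative direction

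*Protocol*

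**What the plan says.** Protocol 6.3 has participants sign a separate consent for intensive PK before randomisation, and then states: "The study will be stratified based on consent to intensive PK (Yes/No) in order to ensure balanced treatment assignment within the intensive PK group". It names no other stratification factor.

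The protocol's own models leave the factor out. For the primary longitudinal analysis (9.4.2): "Model terms will include the respective baseline, treatment, time (ie, cycle), and treatment-time interaction". For the supportive ANCOVA in the same section: "with treatment as a fixed factor and baseline OPP as a covariate".

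The SAP follows the protocol:

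- Section 5.1, where covariates and factors are declared: "The statistical analyses will include treatment, time, and treatment-by-time interaction as factors", and "The baseline value of the endpoint will be included as a covariate".
- Table 2 (estimand and analysis) and section 8.3.5: "Model terms will include the baseline cycle value (mean OPP for BC), treatment, time (i.e., cycle), and treatment-by-time interaction". The example code reads "MODEL CHG = BASELINE TREATMENT CYCLE TREATMENT*CYCLE".
- Section 8.3.7, both supplementary ANCOVAs: "MODEL CHG = BASELINE TREATMENT".
- Section 8.3.6 lists three sensitivity analyses. None adds the stratum.
- Sections 8.4.3 and 8.5.3 define the modelled secondary and exploratory efficacy analyses by reference to 8.3.5 or 8.3.7, so they inherit the same terms.

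The SAP mentions intensive-PK consent only in connection with sampling and the PK analysis sets. It does not say that randomisation was stratified by it, and it gives no reason for leaving it out of the models. The model terms and code are legible, so redaction does not explain the gap.

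**The concern.** When treatment is allocated in balance within strata, differences between strata cancel out of the treatment contrast. A model without the stratum does not know this: it leaves the between-stratum variation in the residual and computes the standard error from it. If the stratum is related to outcome, the reported standard error exceeds the true one, confidence intervals are too wide and the test rejects too rarely under the null. In a proof-of-concept trial the practical consequence is a somewhat higher chance of missing a real effect. The usual practice is therefore to analyse by the factors used to randomise, or to say why not.

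**Working it through.** **Inputs from SAP 4.3:** 95 randomised per group (380 in total), difference 1 point, SD 2.2, two-sided alpha 0.05, dropout 10%, stated power 84%, and at least 10 participants per group in the intensive-PK subset.

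**Assumption:** d, the Yes-minus-No difference in OPP change that remains after baseline adjustment. The documents give no value, so a range is shown.

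**Step 1. Reproduce the stated power.** Evaluable per arm: 95 × 0.9 = 85.5. SE = 2.2 × √(2/85.5) = 0.3365. Power = Φ(1/0.3365 − 1.96) = Φ(1.012) = 84.4% (84.0% with the noncentral t). The SAP's 84% is reproduced.

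**Step 2. Within-stratum variance.** With stratum share p = 10/95 = 0.105, p(1 − p) = 0.0942, and w = 2.2² − 0.0942 d².

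**Step 3. Compare the two models, holding the total SD at 2.2.** Under stratified allocation the true SE of a treatment difference is √(2w/85.5) whichever model is fitted. The model with the stratum reports this value. The model without it reports 0.3365. Hence:

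- SE overstatement without the stratum = 2.2/√w − 1
- Actual alpha without the stratum = 2[1 − Φ(1.96 × 2.2/√w)]
- Power without = Φ((1 − 1.96 × 0.3365)/√(2w/85.5))
- Power with = Φ(1/√(2w/85.5) − 1.96)

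Worked case, d = 1: w = 4.84 − 0.0942 = 4.746, √w = 2.178, true SE = 0.3332. Overstatement = 2.2/2.178 − 1 = 1.0%. Power without = Φ(0.3405/0.3332) = Φ(1.022) = 84.7%. Power with = Φ(3.001 − 1.96) = Φ(1.041) = 85.1%.

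| d (points) | √w | SE too large by | Actual alpha, stratum omitted | Power, omitted | Power, included | Loss (points) |
|---|---|---|---|---|---|---|
| 0 | 2.200 | 0% | 0.0500 | 84.4% | 84.4% | 0 |
| 0.5 | 2.195 | 0.2% | 0.0494 | 84.5% | 84.6% | 0.1 |
| 1 | 2.178 | 1.0% | 0.0478 | 84.7% | 85.1% | 0.4 |
| 2 | 2.113 | 4.1% | 0.0413 | 85.4% | 87.2% | 1.8 |

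**Step 4. Dependence on the stratum share.** Ten per group is a stated minimum. If the share were 30% (an assumption), d = 1 would give actual alpha 0.0451 and power 85.0% against 86.0%; d = 2 would give 0.0311 and 86.7% against 90.5%.

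**Step 5. Simulation check.** Four arms, 40 of 380 in the PK stratum, 10% random dropout, one time point, 20,000 runs. For d = 0, 1 and 2, type I error without the stratum was 0.049, 0.048 and 0.043; with it, 0.049, 0.050 and 0.051. Power without was 84.1%, 84.2% and 84.9%; with it, 84.2%, 84.8% and 86.8%. The simulation agrees with the formulas on direction and size.

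**The case against.** The best defence is that the stratum was never meant as a prognostic factor. Protocol 6.3 gives balance within the intensive-PK group as its purpose. That group serves the noncompartmental analysis set and the PK summaries. It is planned at a minimum of about 10% of participants. The models already adjust for baseline OPP, so only what consent predicts beyond baseline matters. A d of 1 point equals the whole treatment effect the trial is powered for, and 2 points is twice that; smaller values are more natural, and at 0.5 the loss is about 0.1 point. The trial is Phase 2a/b and reports nominal p-values.

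All of this stands as an argument about size, and it is why the point is minor. It does not remove the mismatch, because the stratification constrained allocation for the whole trial. If the sponsor relies on the PK purpose as the reason for omission, the SAP should say so.

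A reader might also argue for more weight on two grounds that fail. One is that consenters cluster at certain sites, which would make the stratum prognostic. Neither document describes who consents or links consent to outcome, and clustering by site would not by itself predict change in OPP. The other is to set the adjusted power against the nominal 84.4%, which suggests losses of 0.7 point (85.1 − 84.4) and 2.8 points (87.2 − 84.4). That comparison is not like for like: once the stratum is prognostic, stratified allocation also raises the power of the unadjusted test, to 84.7% and 85.4%.

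**Conclusion.** The mismatch is certain: the only named stratification factor is absent from every specified efficacy model, without explanation. Its consequence is small. At a 10/95 share, power lost runs from nothing at d = 0 to about 1.8 points at d = 2, and actual alpha from 0.050 down to 0.041. A larger share would raise the loss, as the working shows.

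Three stronger conclusions that a reader might draw are not supported. First, the primary result is not biased: allocation is randomised within strata, so omitting the factor leaves the treatment difference unbiased. Second, type I error is not inflated, since any departure is conservative; nor is the sample size wrong, since the stated 84% reproduces and at d = 0 the required 95 per group does not change. Third, the SAP does not depart from the protocol here, because the protocol's own models omit the stratum too.

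The figures rest on an assumed d, a single time point (TRC3), and SD 2.2 used as the SD of change, as in the sample-size section.

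**What to change.** Add intensive-PK consent (Yes/No, as randomised) as a fixed factor in SAP 5.1, Table 2, 8.3.5 and 8.3.7, and in the CLASS and MODEL statements of the example PROC MIXED code. State that it carries over to the secondary efficacy models defined by reference to those sections. Because the protocol's models also lack the term, record it in SAP section 10, which currently declares no change from the protocol-planned analyses.

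The cost is one model term, about 1 degree of freedom, and some SAP wording. The value is already needed at randomisation, so no new data are collected. The change belongs before unblinding, since SAP 7.2 places the analyses after SAP authorisation, database lock and unblinding, and a covariate added later would look data-driven. If the sponsor prefers to keep the present primary model, the minimum is a sentence giving the reason and one sensitivity analysis that includes the factor.

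Nothing here calls for adding region: it is not a named stratification factor, and SAP 5.2 uses it only for descriptive summaries.

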6.4 Study Treatment Compliance

The prescribed dosage and mode of administration may not be changed. Any deviations from the intended regimen must be recorded in the eCRF.

A record of the quantity of tablets administered by each participant must be maintained and reconciled with study treatment and compliance records.

All study treatment will be administered by the study site staff when the participant is at the site. Any non-compliance will be recorded in the eCRF. Non-compliance is defined as taking any dose (more or less) other than the protocol dose.

6.5 Dose Modification

Dose modifications are not applicable for this study.

6.6 Continued Access to Study Treatment after the End of the Study

The Sponsor will not provide additional care to the participants after they complete or discontinue the study.

